### Aims, purpose, or objectives:

1. To study the feasibility of a wearable brain sensing wellness device to provide mindfulness training to fibromyalgia patients.
2. To assess the association between duration of active state and calm state as measured by the Muse-S™ Headband System, and quality of life (QOL), subjective stress, sleep, and pain in fibromyalgia patients.

The primary outcome will be the change in wide pain index (WPI) and stress over time.

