## Study Design and Methods

### Methods:

All study participants will receive the Muse S™ Headband system and will be asked to use the program daily.

We will assess the following:

- Changes in QOL, sleep, stress, and WPI
- These changes will be measured through week 2, month 1, month 3 and month 6.

	Consent /screen /baseline	Treatment Phase				Follow up Phase
		1	2	3	4	
Visit Type	Face to Face	Phone/ email	Phone/ email	Face to Face/phone/ email	Face to face/phone/ email	
Visit Days	0	14	30	90	180	
Informed Consent	X					
Inclusion/Exclusion	X					
Demographic and History Form	X					
Numeric Pain Intensity Scale (NPIS)	X	X	X	X	X	
Center for Epidemiology Studies Depression (CES-D)	X			X	X	
Widespread Pain Index (WPI)	X			X	X	
Linear Analogue Self-Assessment (LASA - QoL)	X	X	X	X	X	
Stress Scale (PSS)	X	X	X	X	X	
Pittsburgh Sleep Quality index (PSQI)	X	X	X	X	X	
Satisfaction Survey (WIWI)						X
Adverse Events 		X	X	X	X	
Concomitant Medication 	X	X	X	X	X	
Instructions for Muse-S™	X					
End of Treatment/End of Study Forms					X	X

**1** = For visit 5, only serious adverse events will be newly collected; **2** = For visit 5, only newly added concomitant medications for fibromyalgia symptoms will be collected

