A Feasibility Study Evaluating Mindfulness-Based Intervention Assessing A Wearable Wellness Brain Sensing Device (Muse-S™) in Fibromyalgia Patients.

Study Analysis

NCT04720053

06/24/2024

General Study Information

Principal Investigator: [name];

Co-principal investigators: [name]; [name]

Study Title: A Feasibility study evaluating Mindfulness-Based Intervention Assessing A Wearable Wellness Brain Sensing Device (Muse-S™) in Fibromyalgia Patients.

Protocol date of most recent review and approval: 24 June 2024

Data Analysis

Data Analysis Plan:

Demographic characteristics are described using mean and standard deviations or frequencies and percentages based on the type of variable. Differences in WPI and perceived stress were reported as baseline minus the end of study (day 90) value. A linear mixed model with repeated measures for each time point that WPI was taken will be utilized to estimate the association between percent of time spent in calm state with the WPI outcome. For each time interval, the percent of time spent in a calm state will be calculated by taking the average of the calm percentage during the interval. Age, sex, and the total amount of meditation time at each interval will also be adjusted for in the model.

Endpoints:

Primary Hypothesis: With an increase in the percentage of time spent in calm state, the WPI and perceived stress will be lower.

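### The primary hypothesis links calm time to both WPI and perceived stress, but the only calm-state model is for WPI, so the stress half has no planned estimate

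*SAP*

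**What the plan says.** The SAP (Endpoints) gives one primary hypothesis with two outcomes: "With an increase in the percentage of time spent in calm state, the WPI and perceived stress will be lower". Protocol Aim 2 (Aims, purpose, or objectives) seeks the association between time in active and "calm state as measured by the Muse-S™ Headband System, and quality of life (QOL), subjective stress, sleep, and pain in fibromyalgia patients". The same section names change in WPI and stress over time as the primary outcome.

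The SAP (Data Analysis Plan) specifies one association model: "A linear mixed model with repeated measures for each time point that WPI was taken", to estimate "the association between percent of time spent in calm state with the WPI outcome". The exposure for each interval is "calculated by taking the average of the calm percentage during the interval". Age, sex and total meditation time per interval are covariates.

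Perceived stress enters the SAP's analysis text once: "Differences in WPI and perceived stress were reported as baseline minus the end of study (day 90) value".

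The protocol (Methods) lists stress among the changes to be assessed and adds: "These changes will be measured through week 2, month 1, month 3 and month 6". It gives no statistical method for them.

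**The concern.** The hypothesis makes two claims about calm time, and the analysis addresses one. Followed as written, the plan would report a calm slope for WPI and none for perceived stress.

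The planned stress difference cannot fill the gap. The protocol (Methods) states: "All study participants will receive the Muse S™ Headband system and will be asked to use the program daily". A before-after difference in a single group says whether PSS fell on average. It does not say whether patients or periods with more calm time had lower stress, which is what the hypothesis asserts.

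At stake is half of the stated primary hypothesis. An analyst who wanted to fill the gap later would have to choose visits, intervals and adjustment without guidance, possibly with the results in view.

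**Working it through.** The question is whether an analysis is specified. The documents give no alpha, power, effect size or standard deviation, so there is no stated figure to reproduce. The check matches each hypothesised association to a planned analysis and then counts the scheduled data.

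**1. Associations against analyses**

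| Association in the primary hypothesis | SAP analysis of the outcome | Calm term? |
|---|---|---|
| Percent calm and WPI | Mixed model at WPI time points; also baseline-minus-day-90 difference | Yes, in the mixed model |
| Percent calm and perceived stress | Baseline-minus-day-90 difference | No |

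Planned calm-stress estimates: 0. Neither document extends the WPI model to PSS.

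**2. Why the difference does not answer the hypothesis**

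The mean difference is the average over patients of (PSS at day 0 minus PSS at day 90). Percent calm does not appear in it. If the calm scores were reassigned among patients, the result would be unchanged. It therefore carries no information on the calm-stress association.

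**3. Scheduled data**

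Inputs: 43 patients (Protocol, Subject Information); PSS at days 0, 14, 30, 90 and 180 (schedule table in Methods); WPI at days 0, 90 and 180 (schedule table and Assessments); percent calm recorded per session (Server Data).

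- Post-baseline PSS, four visits: 43 x 4 = 172.
- Post-baseline PSS to day 90, three visits: 43 x 3 = 129.
- Post-baseline WPI, two visits: 43 x 2 = 86.

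These are maxima, before dropout and before any interval without a calm score. The outcome with more scheduled follow-up values is the one without a calm model.

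**4. Why the WPI model does not carry over unchanged**

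The WPI model is tied to WPI time points, so post-baseline it covers two intervals: days 0 to 90 and 90 to 180. PSS visits define four: days 0 to 14, 14 to 30, 30 to 90 and 90 to 180. Reusing the WPI time points would drop days 14 and 30, that is 43 x 2 = 86 of the 172 post-baseline PSS values. Using the PSS visits would change the periods over which calm is averaged. The SAP does not make this choice.

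**5. Baseline**

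The first session takes place at the baseline visit (Protocol, Intervention), so no calm score precedes day 0. A day-0 value has no exposure interval in a PSS model, and the same holds in the WPI model.

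**The case against.** The strongest reply is that the same model was plainly meant for both outcomes: the SAP states the exposure, the outcome and the direction for stress in advance. That may be the intention, but the text names WPI as the outcome, ties the model to WPI time points and speaks of a single model. As step 4 shows, carrying it over requires a choice that the SAP does not make.

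Several stronger readings are tempting, and the documents do not support them.

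- A reader might infer that stress is not analysed, or that PSS at days 14, 30 and 180 has no stated use. The SAP plans a difference, and the protocol (Methods) says change in stress will be assessed at week 2 and months 1, 3 and 6. What is missing is a method for the calm-stress association.
- A reader might infer that any later PSS model would be wholly post hoc. The hypothesis was stated in advance; only the model details would come afterwards.
- A reader might infer that only a mixed model will do. Correlating the PSS change with mean percent calm would also address the hypothesis, but that is not planned either.

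It is also fair to say that this is a feasibility study and that the protocol's primary outcome for stress, change over time, has a planned summary. That limits the consequence. It does not supply an estimate for a hypothesis that the SAP itself calls primary.

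**Conclusion.** The point holds. The SAP's primary hypothesis covers two associations, and a calm-state analysis is planned for one of them. The stress half would have no estimate, although up to 172 post-baseline PSS values (129 to day 90) are scheduled and percent calm is recorded per session. This should be corrected because it concerns the primary hypothesis and the repair is cheap.

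The conclusion rests on reading the SAP's model as written, for WPI only. The counts assume 43 enrolled patients with complete follow-up.

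Two limits apply. Which PSS values the difference uses is slightly uncertain, because the SAP calls day 90 the end of study while the protocol (Assessments) calls day 90 end of treatment and day 180 end of study. This does not affect the finding, since neither version has a calm term. Also, Aim 2 speaks of duration of active and calm state and includes QOL and sleep, which have no calm model either. A percent-calm model for PSS would serve the primary hypothesis but not the whole of Aim 2.

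**What to change.** Add to the SAP a linear mixed model for PSS, parallel to the WPI model:

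- **Outcome:** PSS at days 14, 30 and 90 and, if included, day 180. Say whether day 180 is included: the intervention covers the first three months (Treatment phase), but patients keep the headband (Subject Retention).
- **Exposure:** the SAP's interval-average percent calm, over the interval ending at each PSS assessment. State where each interval starts.
- **Adjustment:** age, sex and total meditation time per interval, as in the SAP, plus baseline PSS and visit.
- **Report:** the calm slope with a 95% confidence interval.
- **WPI model:** handle the baseline value in the same way, so that both halves of the hypothesis are tested alike.
- **Two-outcome rule:** state whether both outcomes, or either one, must support the hypothesis.
- **Timing:** if the data have already been analysed, say that the PSS model was specified afterwards although the hypothesis was stated in advance. The SAP mixes past and future tense, so its status is unclear.

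Splitting percent calm into within- and between-patient terms is optional.

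The alternative is to remove perceived stress from the primary calm-state hypothesis and say that Aim 2's stress association will not be estimated.

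Cost: SAP wording, one more model, a two-outcome rule and a matching change to the WPI model. No new visit or questionnaire is needed. The PSS model has six fixed effects before visit (intercept, calm, baseline PSS, age, sex, meditation time), so 6 + 2 = 8 with three visits or 6 + 3 = 9 with four. The alternative costs wording only, but gives up the stress association.
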